5.1.1 Exploratory Cohort

For the Exploratory Cohort, at least 6 subjects who do not have adequate seizure control after they received 1 or more of the following AEDs: PB, MDZ, PHT, LEV, or LDC prior to or at the time of enrollment for the treatment of ENS (first-line, second-line, or subsequent treatment, which may have started prior to the subject's admission into the study site; choice of treatment, dose, and dosing regimen at the Investigator's discretion) will be enrolled. The AED treatment per SOC can be continued when BRV dosing is initiated. Alternatively, another AED treatment (choice of treatment, dose, and dosing regimen at the Investigator's discretion) must be initiated and continue in parallel with BRV treatment.

At any time after AED treatment per SOC for the treatment of ENS (first-line, second-line, or subsequent treatment) was initiated, an initial low dose of BRV (0.5mg/kg [bid]) will be administered at the Investigator's discretion. After the Exploratory Cohort completes the study, a PK and safety data review will be performed by the DMC. During the review of data from the Exploratory Cohort, the enrollment of subjects will be on hold.

At least 2 subjects undergoing hypothermia treatment will be included. Subjects in the Exploratory Cohort might be replaced due to lack of data, as deemed necessary following the review of PK and safety data by the DMC.

The study periods for the Exploratory Cohort are as follows:

- Screening Period: from signing and dating of the written ICF up to initiation of the first BRV dose.

The Screening Period starts up to 36 hours prior to the first administration of BRV. Phenobarbital, MDZ, PHT, LEV, or LDC may have been administered prior to the subject's enrollment into the study and/or at a location other than the study site.

Subjects will enter the Evaluation Period and start BRV treatment as soon as the occurrence of ENS per inclusion criterion 2a is confirmed by the Investigator based on local EEG. If preferred by the Investigator, the central VEEG reader can be consulted to confirm the required ENS.

- Evaluation Period (48 hours): The first BRV infusion marks the starting point of the Evaluation Period. At any time after AED treatment per SOC for the treatment of ENS (first-line, second-line, or subsequent treatment) was initiated, a low dose of BRV (0.5mg/kg) will be administered as an approximately 15-minute iv infusion; additional 3 doses of BRV(0.5mg/kg) can be administered every 12 hours for 48 hours (at the discretion of the Investigator). The AED treatment per SOC can be continued when BRV dosing is initiated. Otherwise, another AED treatment (choice of treatment, dose, and dosing regimen at the Investigator's discretion) must be initiated and continue in parallel with BRV treatment.

Following the first BRV infusion, 3 to 6 PK blood microsamples (60 μ L/sample) will be collected during the 48-hour Evaluation Period from each subject for the determination of

plasma concentrations of BRV and its metabolites, as described in [Table 5–4](#). The first set of 3 PK samples will be collected on the first day within specific timeframes ([Table 5–4](#)), with the second set of 3 PK samples to be collected within the same timeframes on the second day of the 48-hour Evaluation Period. In addition, opportunistic blood samples for the PK analysis may be used at the Investigator's discretion at any time during the Evaluation Period (see [Section 9.1](#)). Blood for PK samples should be drawn from a line different to that of the BRV infusion. The AED PK sample should be collected 3 hours after the start of the initial BRV administration. The number of subjects in the Exploratory Cohort may be increased, if deemed necessary following the analysis of PK data.

At the end of the Evaluation Period, subjects who benefit from BRV treatment may enter the BRV Extension Period in accordance with the Investigator's opinion. Subjects not entering the BRV Extension Period will proceed immediately to the Safety Follow-Up Period (a visit will occur 30 ± 3 days after the final BRV administration).

- BRV Extension Period (up to 28 days of postnatal age [$+7$ days]): Subjects can proceed to the BRV Extension Period if they benefit from BRV treatment during the Evaluation Period, in accordance with the Investigator's opinion. All subjects who participate in the BRV Extension Period must be offered entry into the long-term study, if they meet the eligibility criteria. Subjects will participate in the BRV Extension Period until they reach a stable condition that will allow them to enter the long-term study. The anticipated duration of the BRV Extension Period per subject is up to 28 days of postnatal age ($+7$ days). Subjects must switch to BRV oral solution before entering the long-term study. The timing of the switch from iv to oral solution will be at the discretion of the Investigator; subjects who are not able to be dosed with BRV oral solution when they reach 28 days of postnatal age may continue in the BRV Extension Period for an additional 7 days; subjects who are not able to be switched to BRV oral solution by the end of the additional 7 days of the BRV Extension Period will not be eligible for enrollment in the long-term study.

During the BRV Extension Period, subjects may continue receiving the same BRV dose administered at the end of the Evaluation Period (ie, BRV 0.5mg/kg bid); the BRV dose should not be increased but may be decreased at the discretion of the Investigator.

- Safety Follow-Up Period: Subjects will proceed to the Safety Follow-Up Period if they do not enter the BRV Extension Period. The visit will occur 30 ± 3 days after the final administration of BRV.

5.1.2 Confirmatory Cohorts

For the Confirmatory Cohorts, enrollment will only start after the dosing of BRV is determined based on the PK findings of the Exploratory Cohort and an existing PK model from N01263. A total of at least 36 subjects without adequate seizure control after receiving one or more of the following AEDs prior to or at the time of enrollment: PB, MDZ, PHT, LEV (≤60 mg/kg/day), or LDC (first-line, second-line, or subsequent treatment, which may have started prior to the subject's admission into the study site; dose and dosing regimen at the Investigator's discretion) will enter the Confirmatory Cohorts. The AED treatment can be continued if the subject is on a stable dose for at least 1 hour at the time the first BRV infusion is initiated.

Three consecutive Confirmatory Cohorts (n=12 each) are planned; each cohort must have at least 2 subjects undergoing hypothermia treatment. A PK and safety data review will be performed by

the DMC after completion of each of the 3 Confirmatory Cohorts. Based on the DMC meeting held on 05 Nov 2020, the BRV dose and frequency selected for the Confirmatory Cohorts is 1mg/kg bid (2mg/kg/day). Based on data from the Confirmatory Cohorts, the BRV dose may be further adjusted in a staggered approach as determined by the DMC. During the PK and safety data review of data from the first and second Confirmatory Cohorts, the recruitment of subjects into subsequent cohorts will continue.

The study periods for the Confirmatory Cohorts are as follows:

Screening Period: from signing and dating of the written ICF up to initiation of the first BRV dose.

- The Screening Period starts up to 36 hours prior to the first administration of BRV. Phenobarbital, MDZ, PHT, LEV ($\leq 60\text{mg/kg/day}$), or LDC may have been administered prior to the subject's enrollment into the study and/or at a location other than the study site.
- Baseline Period (included in the Screening Period):
 - For subjects with **intermittent ENS**: at least 1 hour prior to entering the Evaluation Period
 - For subjects in **status epilepticus**: up to 30 minutes prior to entering the Evaluation Period. At least 15 minutes of continuous seizures, or 50% of cumulative seizure activity during a 30-minute interval are to be confirmed on EEG before the administration of BRV can start.

As soon as subjects are considered to be in status epilepticus, steps required for the preparation of the initial BRV infusion can be initiated (eg, assignment of BRV kits through interactive response technology [IRT] and the dilution of BRV solution for iv infusion), even if the required EEG recording is not completed by that time.

Status epilepticus in neonates for the purpose of this study is defined as follows:

- 15 minutes of continuous or cumulative electrographic or electroclinical seizure within 30 minutes

The occurrence of ENS during the Baseline Period must be confirmed either by the local or central VEEG reader prior to BRV administration. Preferably, the central VEEG reader should confirm the required ENS. Video-EEGs that are acquired per standard of care prior to consenting and meet study-specific technical and quality requirements (eg, ability for immediate cloud-based central review) can be used as part of the Baseline assessment VEEG.

- Evaluation Period (96 hours): The first administration of BRV marks the starting point of the Evaluation Period. Subjects in the Confirmatory Cohorts will receive iv BRV 1mg/kg bid (2mg/kg/day), as recommended by the DMC on 05 Nov 2020 based on the results of the PK analysis of the Exploratory Cohort as well an existing PK model from N01263. The DMC will continue to monitor the PK and safety of the subjects and dosing may be adjusted as new data are available. If subjects do not benefit from BRV treatment after 96 hours of BRV administration, BRV administration will be stopped and replaced by another AED.

Following the first BRV infusion, 6 PK blood microsamples (60 μ L/sample) will be collected during the 96-hour Evaluation Period for each subject for the determination of plasma concentrations of BRV and its metabolites, as described in [Table 5–5](#). Blood for PK samples should be drawn from a line different to that of the BRV infusion.

The AED PK sample should be collected 3 hours after the start of the initial BRV administration. In addition, opportunistic blood samples for the PK analysis may be used at the Investigator's discretion at any time during the Evaluation Period (see [Section 9.1](#)).

At the end of the Evaluation Period, subjects who benefit from BRV treatment may enter the BRV Extension Period in accordance with the Investigator's opinion. Subjects not entering the BRV Extension Period will proceed to the Down-Titration Period.

- BRV Extension Period (28 days [up to 90 days] of PNA): Subjects can proceed to the BRV Extension Period if they benefit from BRV treatment during the Evaluation Period, in accordance with the Investigator's opinion. All subjects who participate in the BRV Extension Period must be offered entry into the long-term study, if they meet the eligibility criteria. Subjects will participate in the BRV Extension Period until they reach a stable condition that will allow them to enter the long-term study, if epilepsy is confirmed.

The anticipated duration of the BRV Extension Period per subject is up to 28 (+7) days of PNA. Subjects who are not able to be dosed with BRV oral solution at a PNA of 28 days may continue in the BRV Extension Period for an additional 7 days; subjects who are not able to be switched to BRV oral solution by the end of the additional 7 days of the BRV Extension Period will not be eligible for enrollment in the long-term study.

In the event that a long-term study is temporarily not available, subjects are allowed to remain in the BRV Extension Period until they reach a PNA of up to 90 days. For those subjects, the assessments planned for Unscheduled Visits (see [Section 8.1.3.3](#)) will be conducted in intervals of approximately 30 days during the prolonged Extension Period. The treatment with BRV will be managed through IVRS. Before subjects can roll-over to the long-term study, they must have switched to BRV oral solution.

- Subjects must switch to BRV oral solution before entering the long-term study. The timepoint of the switch from iv to oral solution will be at the discretion of the Investigator.

During the BRV Extension Period, subjects may continue receiving the same BRV dose administered at the end of the Evaluation Period; the BRV dose should not be increased, but may be decreased at the discretion of the Investigator.

Down-Titration Period (up to 1 week): A Down-Titration Period of up to 1 week is recommended for subjects in the Confirmatory Cohorts who discontinue BRV treatment prior to completion of the Evaluation Period, who do not proceed to the BRV Extension Period, or start the BRV Extension Period but do not enter the long-term study. The Down-Titration steps and duration may be adjusted at the Investigator's discretion.

- Safety Follow-Up Period: Subjects will proceed to the Safety Follow-Up Period once they complete the Down-Titration Period. The visit will occur 30±3 days after the final administration of BRV.

Rescue medication should be given if the following occurs:

- There is no improvement in seizure burden within the first 3 hours after administration of BRV.
- Seizure burden is unacceptable to the Investigator, in which case rescue medication can be given earlier at any time, but ideally not in the first 3 hours after the initial administration of BRV.

Subjects in the Confirmatory Cohorts are allowed to switch over from BRV to another AED (eg, MDZ or PHT), if needed. Subjects discontinuing BRV treatment during the Evaluation Period should start the Down-Titration Period while completing the Evaluation Period in parallel for the full 96 hours. In this case, subjects will complete all study assessments, except the collection of blood microsamples for the determination of BRV plasma concentrations. Ideally, changing or adding a new treatment should not occur during the first 3 hours after the initial administration of BRV. Subjects who are switched from BRV to another AED will not be eligible to participate either in the BRV Extension Period or the long-term study.

5.1.3 Study duration per subject

The maximum study duration per subject is expected to be up to 75 days (Screening Period [including Baseline Period (Confirmatory Cohorts only)], Evaluation Period, BRV Extension Period, Down-Titration Period [Confirmatory Cohorts only], and Safety Follow-Up Period). In the event that a long-term study is not available at the time of a subject's planned transition, the maximum study duration for subjects who remain in the study for up to 90 days of PNA and do not enter the long-term study will then be up to 130 days (90 days of PNA, up to 1 week for the Down-Titration Period, and up to 33 days for the Safety Follow-Up Period). The individual study duration will be shorter depending on the type of cohort to which subjects will be assigned, the age at enrollment, and the decision to enter the BRV Extension Period.

The maximum BRV exposure per subject is expected to be up to 42 days, which comprises up to 4 days during the Evaluation Period (depending on type of cohort), up to 28 (+7) days of PNA during the BRV Extension Period, and up to 1 week during the Down-Titration Period for subjects in the Confirmatory Cohorts only. For subjects who remain in the study for up to 90 days of PNA and do not enter the long-term study, maximum BRV exposure per subject is expected to be up to 97 days (up to 90 days of PNA and up to 1 week for the Down-Titration Period).

All subjects who do not continue into the long-term study will proceed to the Safety Follow-Up Period, and a visit will occur 30 ± 3 days after the final dose of BRV.

The end of the study is defined as the date of the last visit of the last subject in the study.

5.1.4 Planned number of subjects and sites

At least 42 evaluable subjects will be enrolled in this study, with at least 6 subjects in the Exploratory Cohort evaluable for the determination of BRV plasma concentrations and at least 36 subjects with evaluable PK data in the Confirmatory Cohorts (at least 12 subjects in each of the 3 Confirmatory Cohorts). At least 2 subjects undergoing hypothermia treatment will be included in the Exploratory Cohort and each of the 3 Confirmatory Cohorts.

The number of subjects in the Exploratory Cohorts might be increased, if deemed necessary, following the analysis of PK data.

5.1.5 Anticipated regions and countries

Only sites in Europe are planned.

5.2 Schedule of study assessments

The schedules of study assessments during the Screening and Evaluation Periods for the Exploratory and Confirmatory Cohorts are presented in [Table 5–1](#) and [Table 5–2](#), respectively. The PK sampling will be performed according to the schedule provided in [Table 5–4](#) for the Exploratory Cohort and in [Table 5–5](#) for each Confirmatory Cohort.

The schedule of study assessments during the BRV Extension, Down-Titration (Confirmatory Cohorts only), and Safety Follow-Up Periods are presented in [Table 5–3](#).

This document cannot be used to support any marketing authorization application and any extensions of variations thereof.
PUBLIC COPY

Table 5–1: Schedule of study assessments – Screening and Evaluation Periods (Exploratory Cohort)

Assessments	Screening Period ^a		Evaluation Period												
	Up to 36h		-36h to 0h	Timepoint immediately before first BRV administration	BRV										
	0h	1h			3h	4h	6h	8h	10h	12h	24h	27h	34h	36h	48h
(Assessment window)	-	-			(±15min)						(±30min)				
Informed consent ^b	X										-X-				
Subject identification card dispensing	X														
Inclusion/exclusion criteria	X	X ^c													
Demographic data	X														
Medical history including Apgar score and HIE	X														
Vital signs		X	X		X		X		X		X	X			X
Physical and neurological examination: Sarnat scale for subjects with HIE		X									X				X
Length		X													
Body weight ^d	X	X									X				X
Head circumference ^e		X													
Primary cause of seizure	X														X
Psychometric parameters: N-PASS and EEG-parameters	X														X
AED treatment (PB, MDZ, PHT, LEV, or LDC)	X ^f										-X-				
Cohort Assignment			X												
BRV infusion			X								X	X			X
Heart rate monitoring		X		X	X	X		X		X	X	X	X	X	X
BRV PK samples ^f			X ^g		X			X			X	X	X		
AED PK sample (only when PB and PHT are used)						X									

Table 5–1: Schedule of study assessments – Screening and Evaluation Periods (Exploratory Cohort)

Assessments	Screening Period ^a		Evaluation Period														
	Up to 36h		Timepoint immediately before first BRV administration	BRV													
	-36h to 0h			0h 1h 2h 3h 4h 6h 8h 10h 12h 24h 27h 34h 36h 48h													
				(±15min)	(±30min)												
(Assessment window)	-	-		-													X
Laboratory assessments (safety)		X ^b															X
Thompson score ⁱ		X															X
Mechanical ventilation																	
AE(s)																	
Concomitant medications																	

^h For Screening and determination of eligibility, use of laboratory data acquired prior to Screening per standard of care inside or outside the study site within 36 hours prior to the start of the Evaluation Period is allowed.

ⁱ Thompson score will be used to measure the severity of HIE for subjects with HIE.

^j The recording of AEDs will include BZDs and opiates taken by the mother at the time of delivery. In addition, details regarding COVID-19 vaccination will be recorded as concomitant medication if the mother was pregnant or breastfeeding when vaccinated.

^k Monitoring for BRV infusion site reactions should take place during and 30 minutes after the end of the infusion.

^l The BRV dosing diary will be dispensed only if the subject enters the BRV Extension Period.

^m Dispensing of BRV is only applicable if the subject enters the BRV Extension Period.

Table 5–2: Schedule of study assessments – Screening and Evaluation Periods (Confirmatory Cohorts)

Assessments	Screening Period ^a		Evaluation Period																		
	Up to 36h																				
	-36h to up to -1h	Base-line Period ^b up to -1h to 0h	0h	3h	6h	8h	9h	10h	12h	15h	18h	21h	24h	27h	34h	36h	48h	60h	72h	84h	96h ^c
			-	-	(±15min)															(±30min)	
(Assessment window)	-	X	-	-	(±15min)																
Informed consent ^d	X	X																			-X-
Subject identification card dispensing	X																				
Inclusion/exclusion criteria	X	X ^e																			

Table 5–2: Schedule of study assessments – Screening and Evaluation Periods (Confirmatory Cohorts)

Assessments	Screening Period ^a		Evaluation Period																			
	Up to 36h		Base-line Period ^b	0h	3h	6h	8h	9h	10h	12h	15h	18h	21h	24h	27h	34h	36h	48h	60h	72h	84h	96h ^c
	-36h to up to -1h	up to -1h to 0h																				
(Assessment window)	-	-	-	(±15min)	(±30min)																	
Demographic data		X																				
Medical history including Apgar score and HIE		X																				
Vital signs		X	X	X	X	X		X	X	X	X	X	X				X		X		X	
Physical and neurological examination: Sarnat scale for subjects with HIE		X												X				X		X		X
Length		X																				
Body weight ^f	X	X												X				X		X		X
Head circumference		X ^g																				
Primary cause of seizure		X																				X
Psychometric parameters: N-PASS and EEG-parameters		X																				X
AED treatment (PB, MDZ, PHT, LEV)	X ^h	X																(X)				

^b The duration of the Baseline EEG depends on seizure activity. Subjects with intermittent seizures will enter the Evaluation Period based on at least 1 hour of EEG recording. Subjects in status epilepticus will enter the Evaluation Period based on up to 30 minutes of EEG recording, ie, as soon as 15 minutes of continuous seizures or 50% of cumulative seizure activity is confirmed on EEG.

^c If subjects do not benefit from BRV treatment after 96 hours of BRV administration, BRV administration will be stopped and replaced by another AED; however, the subject's participation in the study will continue. Subjects discontinuing BRV treatment during the Evaluation Period should start the Down-Titration Period while completing the Evaluation Period in parallel for the full 96 hours.

^d Parent(s) or legal representative(s) will be informed about the study as early as possible and asked to sign the informed consent after the occurrence of seizures is confirmed on VEEG. Continuous consent will be ensured by meetings between the Investigator (or designee) and the subject's parent(s) or legal representative(s), during the conduct of the study.

Table 5–2: Schedule of study assessments – Screening and Evaluation Periods (Confirmatory Cohorts)

Assessments	Screening Period ^a		Evaluation Period																			
	Up to 36h		Base-line Period ^b	0h	3h	6h	8h	9h	10h	12h	15h	18h	21h	24h	27h	34h	36h	48h	60h	72h	84h	96h ^c
	-36h to up to -1h	up to -1h to 0h																				
(Assessment window)	-	-	-	(±15min)											(±30min)							

^c The occurrence of ENS during the Baseline Period must be confirmed either by the local or central VEEG reader prior to drug administration. Preferably, the central VEEG reader should confirm the required ENS.

^f Measurement of body weight is optional at 24, 48, 72, and 96 hours. Dosage of BRV during the Evaluation Period will be based on the subject's weight measured prior to the start of the first BRV administration. However, dosage calculation can be adjusted to a more recent weight measurement, upon discretion of the Investigator, if weight is measured during the Evaluation Period.

^g Head circumference Baseline measurement should be taken within 7 days prior to drug administration, or at birth for subjects ≤7 days old.

^h Subjects will receive iv BRV 1mg/kg bid (2mg/kg/day), as recommended by the DMC on 05 Nov 2020 based on the results of the PK analysis of the Exploratory Cohort as well as an existing PK model from N01263.

ⁱ Video-EEGs that are acquired per standard of care prior to consenting and meet study-specific technical and quality requirements can be used as part of the Baseline assessment VEEG.

^j Following the first BRV infusion, 6 blood microsamples (60µL/sample) will be collected during the Evaluation Period from each subject.

^k The schedule of PK sampling for the Confirmatory Cohorts is also provided in [Table 5–5](#).

^l For Screening and determination of eligibility, use of laboratory data acquired prior to Screening per standard of care inside or outside the study site within 36 hours prior to the start of the Evaluation Period is allowed.

^m Thompson score will be used to measure the severity of HIE for subjects with HIE.

ⁿ The recording of AEDs will include BZDs and opiates taken by the mother at the time of delivery. In addition, details regarding COVID-19 vaccination will be recorded as concomitant medication if mother was pregnant or breastfeeding when vaccinated.

^o Monitoring for BRV infusion site reactions should take place during and 30 minutes after the end of the infusion. The assessment will be conducted hourly from 0h to 3h of the BRV Evaluation Period.

^p The assessment of the Bayley-III score at 96-hour time point only applies to subjects who directly roll-over from the Evaluation Period to the long-term study due to their age at enrollment into N01349.

^q The BRV dosing diary will be dispensed only if the subject enters the BRV Extension Period.

^r Dispensing of BRV is only applicable if the subject enters the BRV Extension Period.

Table 5-3: Schedule of study assessments - BRV Extension Period and Safety Follow-Up Period (Exploratory and Confirmatory Cohorts)

Assessments	BRV Extension Period				Down-Titration Period ^a	Safety Follow-Up Period ^b
	EPV1 ^c	EPV2 ^d	Unscheduled Visit	Telephone Contact		
(Assessment window)	(±2 days)	-			-	(±3 days)
Informed consent ^e	X	X			X	
Vital signs		X	X		X	X
Physical and neurological examination: Sarnat scale for subjects with HIE		X	X		X ^f	X
Biometric parameters: length, body weight and head circumference						X
Primary cause of seizure					X ^f	X
Psychometric parameters: N-PASS					X	X
BRV administration or dispense	X	X ^g			X ^h	
BRV return		X				
1-hour VEEG					X ⁱ	
Laboratory assessments (safety)		X	X ^o			X
Neurodevelopmental testing (Bayley-III score)		X ^j				
AE(s)					-X-	
Concomitant medications					-X-	
Medical procedures					-X-	
AEDs ^k					-X-	

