8.2.1.1 Baseline Period

The Baseline Period will be up to 1 hour immediately prior to the start of initial BRV infusion and depend on seizure activity:

- For subjects with intermittent ENS: at least 1 hour prior to entering the Evaluation Period
- For subjects in status epilepticus: up to 30 minutes prior to entering the Evaluation Period. At least 15 minutes of continuous seizures, or 50% of cumulative seizure activity during a 30-minute interval are to be confirmed on EEG before the administration of BRV can start.

As soon as subjects are considered to be in status epilepticus, steps required for the preparation of the initial BRV infusion can be initiated (eg, assignment of BRV kits through interactive IRT and the dilution of BRV solution for iv infusion), even if the required EEG recording is not completed by that time.

The occurrence of ENS during the Baseline Period must be confirmed either by the local or central VEEG reader prior to drug administration. Preferably, the central VEEG reader should confirm the required ENS. Video-EEGs that are acquired per standard of care prior to consenting and meet study-specific technical and quality requirements (eg, ability for immediate cloud-based central review) can be used as part of the Baseline assessment VEEG.

The following assessments will be performed during the Baseline Period:

- Verification of inclusion/exclusion criteria. Confirmation on VEEG of ≥ 2 minutes of cumulative ENS or ≥ 3 identifiable ENS within the up to 1 hour prior to entering the Evaluation Period (ENS is defined as a seizure lasting for at least 10 seconds on VEEG), despite treatment with one or more AEDs per SOC
- Demographic data
- Medical history (including Apgar score)
- Vital signs (blood pressure, heart rate, respiratory rate [including apneas], oxygen saturation [pulse oximetry], and body temperature)
- Physical and neurological examination (Sarnat scale for subjects with HIE; physical examination will include a check for the presence of skin rash and skin hypersensitivity)
- Length
- Body weight
- Head circumference (Baseline measurement should be taken within 7 days prior to drug administration, or at birth for subjects ≤ 7 days old)
- Primary cause of seizure (HIE, hemorrhage, or infarction; CNS malformations; CNS infections; undetermined causes)
- N-PASS and EEG parameters for the assessment of sedation
- Video-EEG
- Heart rate monitoring

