10.3 Seizure burden

Seizure burden is defined as the total minutes of ENS per hour. Seizure burden information will be recorded for the Confirmatory Cohorts via a continuous VEEG. Seizure burden at Baseline will be evaluated over a period of at least 1 hour (subjects with intermittent seizures) or up to 30 minutes (subjects in status epilepticus).

Electroencephalographic neonatal seizures are defined as EEG seizures occurring for at least 10 seconds.

Seizure counts/seizure burden will be based on data collected using continuous VEEG. The VEEG recording will be evaluated by the local physician or central reader to evaluate eligibility of the subject. The VEEG recordings will subsequently be confirmed and quantified by the central reader at the end of the study.

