3.2.2.2.2 Baseline Period

Baseline Period (-1h to 0h) begins 1 hour before and ends immediately prior to the first initiation of BRV infusion. The Baseline Period is included in the Screening Period.

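### For babies in status epilepticus the protocol takes Baseline burden from a short recording whose length depends on the seizures seen, while the SAP assumes one hour; per recorded minute, the short window lets some unchanged babies count as responders

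*Protocol*

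**What the plan says.** **Entry.** Protocol 5.1.2 defines status as "15 minutes of continuous or cumulative electrographic or electroclinical seizure within 30 minutes". Protocol 8.2.1.1 sets the Baseline Period "For subjects in status epilepticus: up to 30 minutes prior to entering the Evaluation Period", and requires that "At least 15 minutes of continuous seizures, or 50% of cumulative seizure activity during a 30-minute interval are to be confirmed on EEG" before BRV starts. Table 5-2 footnote b lets the baby enter "as soon as 15 minutes of continuous seizures or 50% of cumulative seizure activity is confirmed on EEG".

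**Baseline burden, protocol.** Section 10.3: "Seizure burden at Baseline will be evaluated over a period of at least 1 hour (subjects with intermittent seizures) or up to 30 minutes", the shorter period being for babies in status. Section 4.2.1 expresses burden in minutes per hour, over up to one hour ending at the first dose.

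**Baseline burden, SAP.** Section 3.2.2.2.2: "Baseline Period (-1h to 0h) begins 1 hour before and ends immediately prior to the first initiation of BRV infusion". Section 8.1.2 allows up to one hour. Sections 8.1.5 and 8.2.4 compute change from a one-hour Baseline, and 8.2.4 divides by 1 for the 96-hour variables. Section 8.1.4 divides by the hours in the period concerned.

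**Outcome.** The main responder variable uses a fixed window from 1 to 3 hours after BRV starts. Severe babies need a 50% reduction and nonsevere babies 80%. Under SAP 8.1.2.1 and 8.1.2.2, severe means more than 15 seizure minutes in a 30-minute period; exactly 15 is non-severe.

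**The concern.** The recording that qualifies a baby in status can also be its efficacy Baseline. Its length and timing depend on the quantity being measured; the outcome window does not. A short window placed where seizure activity has just been high will, on average, overstate the usual burden of a baby whose seizures come and go. The later fall towards that usual level then looks like response.

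The study has no concurrent control to absorb this. Protocol 13.5.1 compares the 95% confidence interval of the responder rate with a historical rate and calls BRV efficacious if the lower limit is higher, so an inflated rate bears directly on the conclusion. The sensitivity analysis in SAP 8.2.3 deals with dropout, switching and rescue, not with Baseline length. Because the protocol and the SAP give different windows, two programmers could also derive different responder rates from the same recordings.

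**Working it through.** The documents give no power or sample-size calculation to reproduce. Their one internal figure is consistent: 50% of 30 minutes is 15 minutes.

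**1. When an unchanged baby counts as a responder.** Let B be Baseline burden per recorded hour and μ the true burden. With no drug effect the expected reduction is 1 − μ/B, so a 50% reduction appears when μ ≤ B/2.

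Illustration with assumed numbers: a baby has 24 seizure minutes in the last 30 before BRV, 6 in the 30 minutes before that, and 24 min/h from 1 to 3 hours after.
- Last 30 minutes: B = 24/30 × 60 = 48 min/h. Severe, since 24 > 15. Reduction = (48 − 24)/48 = 50%: responder.
- Last 60 minutes: B = 24 + 6 = 30 min/h. Still severe. Reduction = (30 − 24)/30 = 20%: non-responder.

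**2. Effect of the divisor.** If only the 30 minutes were recorded but divided by one hour, B = 24 min/h and the reduction is (24 − 24)/24 = 0%. With exactly 15 recorded seizure minutes, B = 15 min/h and the baby is non-severe, so response needs 15 × (1 − 0.8) = 3 min/h or less. A fixed one-hour divisor therefore biases Baseline downwards in high-burden babies.

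**3. Simulation with no drug effect.** From the documents: the 15-in-30-minute trigger, the 1 to 3 hour outcome window, the 50% and 80% thresholds and the SAP severity rule. Assumed: exponential seizure and gap lengths, mean seizure 10 or 5 minutes, dosing 10 minutes after the trigger. Baseline ends at dosing and is divided by recorded time. False responders:

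| True burden | 10-min seizures: last 30 min | last 60 min | 5-min seizures: last 30 min | last 60 min |
|---|---|---|---|---|
| 33% | 54% | 26% | 39% | 14% |
| 40% | 41% | 19% | 24% | 9% |
| 50% | 20% | 8% | 7% | 3% |
| 60% | 5% | 2.5% | about 1% or less | about 1% or less |
| 70% or more | under 1% | under 1% | under 1% | under 1% |

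The excess due to the shorter window is the difference between paired columns. For 10-minute seizures it is 54 − 26 = 28, 41 − 19 = 22, 20 − 8 = 12 and 5 − 2.5 = 2.5 percentage points at burdens of 33%, 40%, 50% and 60%. For 5-minute seizures it is 39 − 14 = 25, 24 − 9 = 15 and 7 − 3 = 4 points at 33%, 40% and 50%.

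**The case against.** **The SAP already has the hour.** It names −1h to 0h, and protocol 5.1.2 accepts earlier recordings: "Video-EEGs that are acquired per standard of care prior to consenting and meet study-specific technical and quality requirements" may form part of Baseline. This stands, and it makes the repair easy. It does not settle the matter, because protocol 10.3 still specifies up to 30 minutes and the SAP does not say what to do when less than an hour exists.

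**Early entry is deliberate.** It avoids delaying treatment in status. Agreed; the point concerns only how Baseline burden is derived.

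**Some regression to the mean is unavoidable.** Also true. Seizures are required for entry, and the 60-minute columns are not zero. Only the difference between windows is attributable to the short Baseline.

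**The Full Analysis Set would exclude these babies.** Read literally, its two hours of Baseline VEEG cannot be met with 30 minutes. But the same reading excludes intermittent babies with the one-hour minimum, so it can hardly be the intended rule, and it needs its own correction.

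**Stronger readings that the documents do not support.** A reader might infer that Baseline is inflated for babies in status generally. It is not: the effect nearly vanishes in sustained status, and with a fixed one-hour divisor on a short recording the bias reverses. A reader might also take a baby seizing 15 minutes on and 15 off as an unchanged responder (60 min/h falling to 30). That fails twice. Exactly 15 minutes in a 30-minute period is non-severe and needs 80%; and Baseline runs to the first infusion, not to the moment the trigger is met. For the same reason, rates computed on a window that stops at the trigger do not describe this plan.

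**Conclusion.** The concern holds in a limited form. The protocol and the SAP give different Baseline windows for babies in status, and the choice can change who counts as a responder on the main efficacy variable. With burden per recorded minute, a 30-minute window produces roughly two to three times the false response of a 60-minute window at true burdens of 33% to 50%. At 60% little is left, and at 70% or more almost nothing.

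These figures rest on assumed seizure patterns and an assumed 10-minute delay to dosing. The share of babies in status and their actual patterns are not in the documents, so no inflation of the overall responder rate can be stated. The change should be made before the analysis is run; confidence in the size is moderate.

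**What to change.** Leave the rule for starting BRV as it is. In protocol 4.2.1 and 10.3 and SAP 8.1.2, 8.1.4, 8.1.5 and 8.2.4:

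- Derive Baseline burden for every baby from all interpretable VEEG in the 60 minutes ending at the first infusion, including accepted standard-of-care VEEG from before consent.
- Divide by the time actually recorded, never by a fixed hour.
- Apply the severity classification to that same window.
- Flag babies with less than 60 minutes. Repeat the main responder analysis without them, and report it split by status versus intermittent ENS.

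The cost is wording in both documents and slightly more central reading. Treatment is not delayed. Some babies in status will still have less than 60 minutes, some regression to the mean will remain, and the reported responder rate may be lower.
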